2.2.3 Exploratory endpoints

- To obtain preliminary data of potential biomarkers that would associate with tumor response from the combination of avelumab and intravesical BCG.
- Avelumab combined with intravesical BCG will improve quality of life in patients with NMIBC.

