5.2 Overall Study Design

This is an open-label phase Ib trial of avelumab and intravesical BCG in patients with NMIBC. The study will utilize a modified 3+3 design for potential dose de-escalation in case of patients cannot tolerate to a full dose intravesical BCG. In order to adequately assess safety data at the conclusion of this combination therapy, 3~6 patients will be enrolled at starting dose level (dose level 1). Dose limiting toxicity will be based on the first 6 weeks of proposed study treatment. If 0/3 patients experience a DLT, dose expansion cohort will be activated for additional 15 patients. If 1/3 patients experiences a DLT, the dose level 1 will be expanded to 3 more patients. If 1/6 patients experiences a DLT, the dose expansion cohort will be activated for additional 12 patients. If 2 or more of the 6 patients experience a DLT, the dose level -1 will be evaluated.

At the dose level 1, 3~6 patients will be enrolled to evaluate the safety of proposed combination therapy with standard BCG dosing (50 mg) plus avelumab (10 mg/kg, IV weekly during BCG and every two weeks between BCG). The ability of patients to receive a complete induction course of combination therapy is defined as 5 of 6 weekly treatments of BCG with weekly infusion of avelumab within an 8 week period. Patients will continue maintenance therapy if they tolerate the induction course. Eligible patients will receive avelumab 10 mg/kg, IV weekly dosing plus intravesical BCG 50 mg weekly, 6 weeks on, then 6 weeks off during induction and will continue on a standard maintenance regimen with combination therapy for 1 year. Maintenance therapy beyond 1 year will be at the discretion of the treating physician and will be BCG monotherapy.

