6.3.1 Avelumab

Avelumab will be administered by IV 10 mg/kg over approximately 1 hour at the following schedule:

Induction phase:

- once weekly while receiving BCG treatment
- once every 2 weeks after BCG treatment is completed

Maintenance phase:

- Once weekly during BCG
- Once every 2 weeks after completion of BCG

One cycle = 12 weeks (84 days). A standard maintenance therapy regimen will be provided with BCG occurring at Month 3, 6, and 12. Avelumab treatment ends at the conclusion of Month 12 maintenance therapy. In both the induction and maintenance phases, no avelumab will be administered the week following BCG therapy completion. The subsequent every two week avelumab dosing will begin following this one week period.

For administration in clinical trials, avelumab drug product must be diluted with 0.9% saline solution (sodium chloride injection) supplied in an infusion bag; alternatively, a 0.45% saline solution can be used if needed. The verified avelumab concentration range in the infusion solution is 0.016 mg/mL to 8 mg/mL.

The investigator and team should make every effort to target infusion timing to be as close to 1 hour as possible. However, given the variability of infusion pumps from site to site, time windows of -10 minutes and +20 minutes are permitted (i.e., 50–80 minutes). The exact duration of infusion should be recorded in both source documents and CRFs.

In case prepared dosing solution cannot be administered immediately after preparation, the acceptable holding time is: no more than 4 hours at room temperature (15-25°C, 59-77°F), including infusion time, or no more than 24 hours under refrigerated conditions (2-8°C, 36-46°F), including infusion time.

If stored under refrigerated conditions, allow each bag to equilibrate to room temperature (15-25°C, 59-77°F), preferably for one hour before administration.

Premedication with an antihistamine and with acetaminophen (for example, 25 – 50 mg diphenhydramine and 500 – 650 mg acetaminophen IV or oral equivalent) approximately 30 to 60 minutes before each dose of avelumab is mandatory. This regimen may be modified based on local treatment standards and guidelines as appropriate provided it does not include systemic corticosteroids.

During the treatment between BCG, avelumab may be administered up to 2 days before or after each scheduled treatment day for administrative reasons, except for day 1 of BCG induction phase and C1D1 of BCG maintenance phase.

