6.4.2.2 Toxicity management

Methods to improve patient's symptoms such as use of anticholinergics or antibiotics is allowed at the treating physician's discretion as per usual standard of care. Recommendations for management of Intravesical BCG-specific toxicities are shown in **Table 6**.

Table 6 Intravesical BCG related symptom alleviation and toxicity management

Toxicity	Recommendations
Transient symptoms: urinary frequency, urgency, dysuria, cystitis, malaise, fever < 38.5°C	Expected after intravesical BCG and usually resolves within 48 hrs. Consider symptomatic treatment (anticholinergics, pyridium, acetaminophen). Consider urine culture. Continue intravesical BCG treatment.
Persistent (> 48hr) fever < 38.5°C, cystitis, malaise	Urine culture; hold BCG until symptoms subside.
Fever > 38.5°C for 12-24 h	Urine culture; if culture is negative, consider Isoniazid 300 mg daily for 3 months; May resume intravesical BCG when asymptomatic.

Toxicity	Recommendations
Acute severe illness, local or systemic pneumonitis, hepatitis, prostatitis, ureteral obstruction, renal abscess, persisting high fever > 39°C	Isoniazid 300 mg, rifampin 600 mg and/or ethambutol 1200 mg, daily for 6 months; Discontinue intravesical BCG.
Sepsis	Isoniazid 300 mg, rifampin 600 mg and/or ethambutol 1200 mg daily for 6 months; cycloserine 500 mg twice daily orally; high-dose corticosteroids immediately; Discontinue intravesical BCG.

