- b. If history, PE, ECOG-PS and screening laboratory tests are performed within 72 hours prior to first dose (Cycle 1, Day 1), repeat testing is not required.
- c. Tumor assessment via CT or MRI will be optional at screening if data from standard care is available.
- d. **Toxicity assessment is required prior to each BCG and/or avelumab treatment.** If dose interruption or modification is required at any point on study because of hematologic toxicity, weekly CBC will be monitored until the AE resolves, and to ensure safety of the new dose, weekly blood draws for CBC will be also required for an additional 4 weeks after the AE has been resolved to the specified levels, after which monitoring every 3 weeks may resume.
- e. Consisting of albumin, alkaline phosphatase, BUN, calcium, carbon dioxide (CO₂), chloride, creatinine, glucose, potassium, AST, ALT, sodium, total bilirubin, total protein
- f. Patients will undergo EKG monitoring at screening. Additional EKG at pre-dose on day 1 of each cycle and EOT if clinical indicated.
- g. Blood sample for exploratory biomarkers will be collected at pre-dose on day 1 of induction therapy; and at pre-dose on day 1 of month 3 and month 6 maintenance therapy.
- h. Urine sample will be collected at pre-dose on days 1, 22 and 43 of induction treatment; and at pre-dose on day 1 of Months 3 and 6 Maintenance for measurement by multiplexed immunoassay for immune response biomarkers.
- i. Cystoscopy and urine cytology will be obtained at screening and at Month 3, 6, 9, and 12 and at EOT. Only frankly malignant cytology will be considered positive and used to determine the need for bladder biopsy and further evaluation.
- j. Patient will be asked to complete EORTC QLQ-C30 to measure QOL on BCG [33].
- k. Every three months for up to one year. See Sections 7.2.1 and 7.2.2 for additional details.
- l. During the COVID-19 crisis, protocol mandated visits may be performed via telemedicine or visits may be combined in order to prevent imminent safety risks to patients. All such changes to the visit schedule must be clearly documented in the subject's chart. Changes in study visit schedules or missed visits must be explained in the final clinical study report.

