The EORTC QLQ-C30: is a 30-item cancer-specific quality of life questionnaire developed to assess QOL endpoints [33]. The measure consists of 5 functional scales (physical, role, cognitive, emotional and social), 3 symptom scales (fatigue, pain, and nausea/vomiting), a global health status / quality of life scale, and additional symptoms commonly reported by cancer patients (dyspnoea, loss of appetite, insomnia,

constipation and diarrhea) and perceived financial impact of the disease (<https://www.eortc.be/qol/files/SCManualQLQ-C30.pdf>). The EORTC QLQ-C30 is reliable and has discriminatory association with clinical status, disease stage, and symptom severity. Patients are asked to answer questions regarding their symptoms and/or quality of life on day 1 prior to BCG treatment during BCG induction phase and day 1 of BCG maintenance phase.

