- xxvii. Administration of a live/attenuated vaccine within 4 weeks prior to the first dose of study treatment, within 5 months following the administration of the last dose of study drug, or anticipation that such a live/attenuated vaccine will be required during the study.
- xxviii. Other severe acute or chronic medical conditions including immune colitis, inflammatory bowel disease, immune pneumonitis, pulmonary fibrosis or psychiatric conditions including recent (within the past year) or active suicidal ideation or behavior; or laboratory abnormalities that may increase the risk associated with study participation or study treatment administration or may interfere with the interpretation of study results and, in the judgment of the investigator, would make the patient inappropriate for entry into this study.

5. Analysis Populations

The analysis populations are defined as below.

- a. **Safety population:** All patients who receive at least one dose of combination avelumab and BCG will be included in the analyses of compliance and safety.
- b. **Biomarker population:** For biomarker analysis, the biomarker population will comprise all evaluable patients who have sufficient baseline and on-study biomarker measurements.
- c. **Evaluable population:** Evaluable patients will be defined as patients who receive at least 5 doses of intravesical BCG and avelumab IV weekly during induction treatment and complete the first post-treatment cystoscopy and/or urine cytology for tumor assessment. Patients

who discontinued study treatment due to toxicity incurred by previous therapy will be evaluated for safety analysis, but will be replaced by additional patients for the efficacy analysis.

Patients removed from study for early withdrawal or hypersensitivity reactions will be replaced if they have received less than 5 doses of study treatment during induction treatment, but will be included in the safety analysis.

Patients who do not receive at least 5 doses of intravesical BCG and avelumab IV during induction treatment will be considered unevaluable for efficacy analysis and will be replaced unless the missed doses were due to development of grade 3-4 adverse events related to study treatment.

Evaluable population will be used for the analysis of EORTC QOQ-C30 (Section 6) and antitumor measures (Section 8).

6. Patient Population Summary

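### Apart from end of treatment, quality of life is scheduled only before BCG courses, so the weekly induction phase is not measured, and the SAP analyses a narrower set of patients than the protocol

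*Protocol*

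**What the plan says.** **Purpose.** Protocol 2.1.3 makes the impact of the combination on quality of life a separate patient-reported objective. The matching endpoint is listed as exploratory in 2.2.3: "Avelumab combined with intravesical BCG will improve quality of life in patients with NMIBC". Table 7, footnote j, gives the aim of the form: "Patient will be asked to complete EORTC QLQ-C30 to measure QOL on BCG".

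**Timing.** Section 8.2 reads "Patients are asked to answer questions regarding their symptoms and/or quality of life on day 1 prior to BCG treatment during BCG induction phase", and adds Day 1 of the maintenance phase. Table 7 has three marks in the quality-of-life row. By column position they are induction Day 1, maintenance Day 1 and EOT. Section 8.2 does not mention EOT. Neither place has a form on induction Days 22, 43 or 64, or later within a maintenance cycle.

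**Regimen.** Section 5.2 describes treatment as "6 weeks on, then 6 weeks off during induction", and Section 6.3.1 gives "One cycle = 12 weeks (84 days" as the cycle length. Avelumab is weekly during BCG and every two weeks between courses.

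**Analysis set.** SAP 5.c: "Evaluable population will be used for the analysis of EORTC QOQ-C30 (Section 6) and antitumor measures (Section 8". That population needs at least 5 induction doses of both agents and a first post-treatment cystoscopy and/or cytology. An exception covers doses missed because of related grade 3-4 adverse events. Protocol 10.2, where the QLQ-C30 summary is planned, limits the analysis to the Section 8.1.1 set: at least one dose of BCG and avelumab.

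**Method.** Both documents say only that the scales will be summarised. SAP Section 10 rules out imputation.

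**The concern.** The treatment under test is most intense in the weekly BCG plus avelumab weeks, above all the six weeks of induction, and tolerability of induction is the primary objective. The form meant to record how patients feel on BCG is given before induction starts and then not until the first maintenance course is due. Whatever patients experience in the weekly phase is seen only if it persists into the following weeks.

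The analysis set adds to this. A patient who gives up induction after three or four doses because of lower-grade symptoms is the kind of patient a quality-of-life measure should describe. Under SAP 5.c that patient is left out.

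Both choices lean towards a favourable picture, and the endpoint is already worded as a favourable conclusion. At stake is a published statement that quality of life was maintained or improved, resting on forms taken between BCG courses by patients who mostly got through induction.

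**Working it through.** **1. Cycle length.** 6 weeks on + 6 weeks off = 12 weeks; 12 × 7 = 84 days. This reproduces the figure in Section 6.3.1.

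**2. Calendar.** Day 1 of cycle k = 84 × (k − 1) + 1. Table 7 puts maintenance BCG in cycles 2, 3 and 5, hence Days 85, 169 and 337. Table 1 gives six weekly induction doses (Days 1, 8, 15, 22, 29, 36) and three weekly doses per maintenance course (85, 92, 99; 169, 176, 183; 337, 344, 351).

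**3. Nominal gaps.** Gap = day of form − day of last preceding instillation.

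| Form | Last instillation | Gap |
|---|---|---|
| Day 1 (baseline) | none on study | – |
| Day 85 (Month 3) | Day 36 | 85 − 36 = 49 days (7 weeks) |
| Day 169 (Month 6) | Day 99 | 169 − 99 = 70 days (10 weeks) |
| Day 337 (Month 12) | Day 183 | 337 − 183 = 154 days (22 weeks) |
| EOT, completers | Day 351 | not fixed by the documents |

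**4. Permitted delays.** Visits are anchored to Cycle 1 Day 1, so a late induction shortens the first gap.

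- Last instillation in week 8 (Day 50 to 56): 85 − 50 = 35 days, down to 85 − 56 = 29 days.
- A full 21-day interruption (Section 6.1): 36 + 21 = Day 57, and 85 − 57 = 28 days.
- With the visit 3 days early (footnote a): 28 − 3 = 25 days.

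The first gap is therefore 7 weeks nominally and about 4 weeks in the late case. The separate 10-day allowance for unforeseen events is not counted.

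**5. Who is in the analysis.**

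| Patient | SAP 5.c | Protocol 10.2 with 8.1.1 |
|---|---|---|
| Under 5 doses, lower-grade intolerance | out | in |
| Under 5 doses, early withdrawal | out | in |
| Under 5 doses, removed for hypersensitivity | replaced (no grade stated) | in |
| Under 5 doses, related grade 3-4 event | kept by the exception | in |
| 5 or more doses, no tumour assessment | out | in |

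The protocol column assumes at least one dose of each agent. The documents give no expected number for any row.

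**6. Timing of forms at existing visits.** Induction Day 22 before dosing: 22 − 15 = 7 days after an instillation. Induction Day 43: 43 − 36 = 7 days. Day 22 of a maintenance course, whose last dose is on its Day 15: 22 − 15 = 7 days. All three lie in the weekly phase or one week after it.

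**The case against.** Several stronger readings are tempting, and the documents do not support them.

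- **No form ever follows weekly treatment.** A reader might infer this from Section 8.2, but Table 7 has an EOT form. Under Section 6.6 avelumab ends with the Month 12 course, so for completers EOT follows three weekly combination doses. For early stoppers it follows stopping. It still says nothing about induction in those who continue.
- **The forms are always at least seven weeks after BCG.** Seven weeks is the smallest nominal gap before a course, not a floor; step 4 gives about four.
- **Only patients who tolerated induction are analysed.** SAP 5.c keeps those whose missed doses were due to related grade 3-4 events, and protocol 10.2 points to a wider set. This is an unresolved conflict with a narrow SAP rule, not a settled exclusion of all intolerant patients. The protocol also describes the form within Section 8.2, whose subsection 8.2.1 carries the narrower efficacy definition, so the SAP's choice has some basis.
- **The trial cannot show any effect on quality of life.** Avelumab continues between courses, so the pre-course forms do describe change from baseline on avelumab. Attribution fails because there is one arm, whatever the timing.

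The symptom argument also has limits. Table 6 says of transient BCG symptoms: "Expected after intravesical BCG and usually resolves within 48 hrs". A form seven days after an instillation would miss many of these too, and the QLQ-C30 scales listed in Section 8.2 include no urinary scale. Table 6 does have a separate row for symptoms lasting beyond 48 hours.

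Finally, quality of life is exploratory and drives no decision. Severe intolerance is captured by the primary endpoint, the dose-limiting toxicity rules, toxicity checks before each dose and adverse event tables. That lowers the stakes, but it does not supply the patient-reported information that objective 2.1.3 asks for.

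**Conclusion.** The point holds in a limited form. Between the pre-dose form on Day 1 and the Month 3 form on Day 85, patients who stay on treatment have no quality-of-life assessment, so the six weekly induction treatments go unmeasured. The pre-course forms sit nominally 49, 70 and 154 days after BCG, the first falling to about 4 weeks with permitted delays. The plan can describe quality of life between BCG courses and at EOT. It does not describe the weekly induction phase, although footnote j names quality of life on BCG as the aim.

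Separately, the SAP's set omits early stoppers with lower-grade intolerance, hypersensitivity or withdrawal, and disagrees with protocol 10.2 and 8.1.1. The direction of the resulting bias is towards patients who tolerated treatment; its size cannot be given from the documents.

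Assumptions: Months 3, 6 and 12 are Day 1 of cycles 2, 3 and 5; the Table 7 marks are read by column position in extracted text; and Section 8.2 means Day 1 of every maintenance course. If it means only the first, the Month 6 and Month 12 forms do not exist and coverage is thinner still.

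This is worth correcting, but it does not touch the primary analysis.

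**What to change.** 1. **Analysis set (SAP 5.c and 6).** Analyse the QLQ-C30 in all treated patients with a baseline form, in line with protocol 10.2 and 8.1.1. Report change from baseline by visit, with the number of forms received at each. This needs wording only.
2. **Schedule (Table 7 and Section 8.2).** Add the form at visits Table 7 already lists: induction Day 22 and/or Day 43, and Day 22 of each maintenance course. Report these separately from the pre-course forms.
3. **EOT.** Make Section 8.2 and Table 7 agree on whether an EOT form is collected, and say when it falls relative to the last instillation.
4. **Endpoint 2.2.3.** Reword as change from baseline in QLQ-C30 scales. A single arm cannot show that the combination improves quality of life.

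The cost is a 30-item form at a few existing visits, with no new visits. The gain is also limited: forms about seven days after an instillation may still miss symptoms that clear within 48 hours, and the instrument has no urinary scale. What is gained is information on the global, functional and general symptom scales during the weekly phase, and a summary that no longer leaves out treated patients who stopped early.

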8.2.1 Definition of Evaluable Patients for Efficacy Analysis

Evaluable patients will be defined as patients who receive at least 5 doses each of intravesical BCG and avelumab IV during induction treatment (first 8 weeks) and complete the first post-treatment cystoscopy and/or urine cytology for tumor assessment. Patients who discontinued study treatment due to toxicity incurred by previous therapy will be evaluated for safety analysis, but will be replaced by additional patients for the efficacy analysis.

Patients removed from study for early withdraw or hypersensitivity reactions will be replaced if they have received less than 5 doses of study treatment during induction treatment, but will be included in the safety analysis.

Patients who do not receive at least 5 doses of intravesical BCG and avelumab IV during induction treatment will be considered unevaluable for efficacy analysis and will be replaced unless the missed doses were due to development of grade 3-4 adverse events related to study treatment.

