a repeat induction of BCG for patients with disease refractory to the first BCG induction only has a response rate of around 20%. Cystectomy is offered to patients who have high risk NMIBC and those who may be resistant to BCG. However, few patients want to undergo such a radical surgery. Improvements in BCG treatment, particularly the addition of systemic immunotherapy may lead to improved response rates, decreased rates of recurrence and better survival without the need for cystectomy.

Patients undergoing BCG therapy must be able to tolerate induction therapy. For any strategy to improve the anti-cancer efficacy of intravesical BCG completion of induction therapy is required. This study includes a safety lead-in to ensure patients tolerate the combination therapy of full dose BCG and a novel weekly dosing of avelumab. BCG has been shown to be effective in split dosing. If patients are not tolerant of full dose BCG, reduced dosing will be evaluated. For this study to proceed, patients must be able to tolerate induction therapy as commonly defined as receiving at least 5 of 6 weekly treatments within an 8 week period. The completion of a full induction course within eight weeks of starting treatment is the primary endpoint of this study. Patients who cannot tolerate 5 of 6 weekly treatments as part of induction therapy will be considered treatment failures.

The response to treatment at the 6 month mark has been shown to be predictive of further tumor recurrence [11]. A secondary endpoint of this study will be the rate of completion of the 6 month maintenance course which will simultaneously evaluate for tolerance of therapy at 6 months and disease response. This measure will provide a clinically meaningful endpoint of both safety and efficacy.

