5.2.1 Definition of Dose limiting toxicity

During safety lead-in phase, Dose limiting toxicity (DLT) will be monitored during the first 6 weeks of the combination avelumab and intravesical BCG. DLTs will be defined as any and all adverse events at least possibly related to study drug which occur in the DLT evaluation period and meet the criteria below, as evaluated by the NCI-CTCAE version 5.0.

Note: DLTs and other toxicities will be discussed between the Principal Investigator, and the Data Safety Monitoring Committee (DSMC). The discussions are the basis for the decisions regarding dose expansion (or de-escalation) according to the rules of the protocol.

DLT will be classified as either hematologic or non-hematologic toxicity (assessed in accordance with the CTCAE Version 5.0 criteria).

The following are DLTs:

1. Toxicity causing greater than 2 weeks of dose delay. For example, if a subject has dose delay greater than 2 weeks due to an AE, such AE is a DLT.
2. Grade 4 neutropenia greater than 5 days.
3. ALT/AST $> 3x$ ULN with bilirubin $> 2x$ ULN without another explanation (e.g., cholestasis)
4. Any Grade 3 hypersensitivity reaction is a DLT
5. Grade 4 thrombocytopenia of any duration
6. Grade 3 thrombocytopenia with significant hemorrhage of any duration
7. Febrile neutropenia

And, any non-hematological Grade ≥ 3 toxicities will be a DLT.

The following may be considered as exceptions to DLTs:

1. Grade 3 nausea, vomiting, or diarrhea and Grade 4 vomiting or diarrhea in the absence of maximal medical therapy that resolves in 72 hours
2. Grade 3 fatigue lasting < 5 days
3. Grade 3 hypertension that can be controlled with medical therapy
4. An increase of indirect (unconjugated) bilirubin indicative of Gilbert's syndrome
5. Serum lipase and/or serum amylase CTCAE Grade 3 ≤ 7 consecutive days without clinical signs or symptoms of pancreatitis

5.2.1.1 Definition of DLT Evaluable Population:

Patients enrolled in safety lead-in cohort who receive at least 4 doses and complete the DLT observation period (the first 42 days of induction treatment), unless the patient discontinued the study treatment due to a DLT.

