Grade 2 Therapy or infusion interruption indicated but responds promptly to symptomatic treatment (eg, antihistamines, NSAIDs, narcotics, IV fluids); prophylactic medications indicated for ≤ 24 hours.	
 Stop avelumab infusion. Resume infusion at 50% of previous rate* as soon as infusion-related reaction has resolved or decreased to at least Grade 1 in severity, and monitor closely for any recurrence or worsening.
Grade 3 or Grade 4 – severe or life-threatening Grade 3: Prolonged (eg, not rapidly responsive to symptomatic medication and/or brief interruption of infusion); recurrence of symptoms following initial improvement; hospitalization indicated for clinical sequelae. Grade 4: Life-threatening consequences; urgent intervention indicated.	
 Stop avelumab infusion immediately and disconnect bag infusion tubing from the patient. Avelumab treatment must be permanently discontinued.

*If avelumab infusion rate has been decreased by 50% due to an infusion reaction, it must remain decreased for the next scheduled infusion. If no infusion reaction is observed at the next scheduled infusion, the infusion rate may be returned to baseline at subsequent infusions.

In the event of a Grade 2 infusion-related reaction that does not improve or worsens after implementation of the modifications, the Investigator may consider treatment with corticosteroids, and the infusion should not be resumed for that cycle. At the next cycle, the Investigator may consider the addition of H2-blocker antihistamines (eg, famotidine or ranitidine), meperidine, or ibuprofen to the mandatory premedication.

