6.7 Treatment Discontinuation

Patients must permanently discontinue study treatment (avelumab and BCG) if they experience any of the following:

- Intolerable toxicity related to study treatment, including development of an immune mediated adverse event determined by the investigator to be unacceptable given the individual patient's potential response to therapy and severity of the event
- Any medical condition that may jeopardize the patient's safety if he or she continues study treatment
- Investigator determines it is in the best interest of the patient
- Use of another non-protocol anti-cancer therapy
- Pregnancy
- Loss of clinical benefit as determined by the investigator after an integrated assessment of cystoscopy, radiographic and local biopsy results (if available), and clinical status (e.g., symptomatic deterioration such as pain secondary to disease)
- Patients have Cystoscopy or Radiographic disease progression or symptomatic deterioration attributed to disease progression

The primary reason for study treatment discontinuation should be documented in the patient's medical records. Patients who discontinue study treatment prematurely will be replaced.

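### Protocol 8.2.1 and SAP 5.c give opposite replacement rules for a patient removed before 5 doses for a related grade 3-4 hypersensitivity reaction, and neither says how a patient who is not replaced is scored.

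*Protocol*

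**What the plan says.** Four places bear on this patient.

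- **Protocol 8.2.1, paragraph 2:** "Patients removed from study for early withdraw or hypersensitivity reactions will be replaced if they have received less than 5 doses of study treatment". No grade or relatedness limit is attached. The same sentence keeps these patients in the safety analysis.
- **Protocol 8.2.1, paragraph 3:** patients with fewer than 5 doses of BCG and avelumab in induction are unevaluable for efficacy and "will be replaced unless the missed doses were due to development of grade 3-4 adverse events related to study treatment". There is no carve-out for hypersensitivity.
- **SAP 5.c (Evaluable population):** both rules again. The first reads "Patients removed from study for early withdrawal or hypersensitivity reactions will be replaced if they have received less than 5 doses of study treatment". SAP 5.c then assigns this population to the quality-of-life analysis and to all of SAP Section 8.
- **Protocol 6.7:** "Patients who discontinue study treatment prematurely will be replaced". No exception is given for any toxicity.

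Protocol 10.2 restricts the statistical analysis to the set in 8.1.1, which needs only one dose of BCG and avelumab.

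The plan treats the event as a toxicity of the regimen. For the lead-in, Protocol 5.2.1 says "Any Grade 3 hypersensitivity reaction is a DLT". On non-completion in general, Protocol 1.2 says "Patients who cannot tolerate 5 of 6 weekly treatments as part of induction therapy will be considered treatment failures".

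**The concern.** The third paragraph of 8.2.1 has a clear purpose: a patient lost to serious toxicity from the study treatment should not be exchanged for a fresh one. The second paragraph can undo this for a toxicity the plan anticipates. Protocol 1.4.2 names infusion-related reactions, including hypersensitivity, as an important risk of avelumab. For grade 3-4 infusion-related reactions, Table 3 in Protocol 6.4.1 says "Avelumab treatment must be permanently discontinued", and this can happen before the fifth dose.

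The study is open-label and single-arm. If the rule is left open, someone will decide whether to replace such a patient after seeing what happened to that patient. A choice to replace removes a treatment-caused failure from the efficacy denominator.

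**Working it through.** **1. Each rule applied to the same patient** (removed before 5 doses, related grade 3-4 hypersensitivity reaction)

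| Source | Replaced? | In the efficacy denominator? |
|---|---|---|
| Protocol 8.2.1 para. 2 and SAP 5.c | Yes | No |
| Protocol 8.2.1 para. 3 and SAP 5.c | No | Not stated; para. 1 requires 5 doses of each drug |
| Protocol 6.7 | Yes | Not stated |
| Protocol 10.2 (set of 8.1.1) | Not addressed | Yes |

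The replacement rules conflict, and no order of precedence is given in either document.

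**2. The plan's own precision figure.** Protocol 10.1 and SAP 3.b give a Wilson lower bound of 37.6% for n = 18 and p = 0.60.

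- Centre = (p + z²/2n)/(1 + z²/n) = (0.60 + 0.1067)/1.2134 = 0.5824.
- Half-width = z·√(p(1−p)/n + z²/4n²)/(1 + z²/n) = 1.96 × √(0.01333 + 0.00296)/1.2134 = 0.2062.
- Interval: 37.6% to 78.9%. The stated bound is reproduced and is not in dispute.

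**3. Effect of replacement on an 18-patient rate.** The documents give no expected CR rate, so p = 0.40 to 0.60 is an assumption. The upper value borrows the plan's expected Month 6 completion rate. Let k patients have the event.

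- Replaced: expected rate = p.
- Kept and scored as failures: expected rate = p(18 − k)/18.
- Difference = pk/18.

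| p | k | Replaced (Wilson 95%) | Kept as failure (Wilson 95%) | Difference (points) |
|---|---|---|---|---|
| 0.40 | 1 | 40.0% (21.1-62.4) | 37.8% (19.5-60.4) | 2.2 |
| 0.40 | 2 | 40.0% (21.1-62.4) | 35.6% (17.9-58.3) | 4.4 |
| 0.60 | 1 | 60.0% (37.6-78.9) | 56.7% (34.7-76.3) | 3.3 |
| 0.60 | 2 | 60.0% (37.6-78.9) | 53.3% (31.8-73.7) | 6.7 |

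There is a third outcome: not replaced, but still unevaluable. The denominator falls to 17 for k = 1 and the expected rate stays at p. At p = 0.60 the interval is 37.0-79.3%.

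**4. How often the case might arise.** The documents give no grade 3-4 hypersensitivity rate for weekly dosing. Two every-2-week cohorts in Protocol 1.4.2 help a little.

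- 88 patients: the grade 3 treatment-related events listed are lymphopenia, creatine phosphokinase, aminotransferase and cholesterol increases, with no grade 4 events. That is 0/88 for infusion reactions.
- 44 patients: the grade 3-4 events named are asthenia, AST elevation, creatine phosphokinase elevation and decreased appetite. If that list is complete, this is 0/44. The 20.5% infusion-reaction rate is for any grade.

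Pooled 0/132 has a one-sided 95% upper bound of 1 − 0.05^(1/132) = 2.2%. At that bound, the chance of at least one such patient in 18 is 1 − 0.05^(18/132) = 33.5%. At other assumed rates, 1 − (1 − q)^18 gives 16.5% for q = 1%, 30.5% for 2% and 60.3% for 5%. The 5% row has no support in the documents and only shows sensitivity, since weekly dosing could differ.

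**The case against.** The strongest reply is that paragraph 2 is the specific rule and paragraph 3 the general one, so paragraph 2 governs. That is plausible, but neither document says so. It would also confirm that a treatment-caused failure is exchanged for a new patient.

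Several limits stand:

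- Paragraph 2 covers patients removed from study. Protocol 6.4 allows BCG to continue while avelumab is held, so not every reaction leads there.
- The efficacy analyses are secondary, with no hypothesis test and a sample size set by feasibility. A shift of 2-3 points is small against an interval of roughly 38-79%.
- If Protocol 10.2 is followed, the patient stays in the analysis and no inflation arises.

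Stronger readings that a reader might infer, and why they fail:

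- **That hypersensitivity is the only related grade 3-4 toxicity whose patient is replaced.** This is so within 8.2.1 only. Protocol 6.7 replaces everyone who stops early.
- **That the serious infusion-related reaction in the 88-patient study gives a grade 3-4 rate of 1.1%.** Serious is not a grade, and that study's grade 3 list contains no infusion reaction.
- **That the risk is hidden from the trial.** Both documents keep these patients in the safety analysis. Protocol 5.2.1.1 keeps patients who stop for a DLT in the DLT-evaluable set.
- **That the primary endpoint is inflated.** SAP 8.a places induction completion in the section to which SAP 5.c applies the evaluable set, so a literal reading reaches it. But SAP 5.a assigns compliance to the safety population, Protocol 10.2 uses the one-dose set, and Protocol 1.2 calls non-completers failures. The texts leave this unsettled.

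**Conclusion.** The contradiction is real, sits in both documents and has no stated resolution. Protocol 6.7 and 10.2 add two further answers that do not agree. If the patient is replaced and the SAP evaluable set is used, the expected 18-patient rate is 2.2-3.3 points higher per patient than if that patient were kept as a failure. This rests on an assumed 40-60% success rate in the replacement and on scoring the kept patient as a failure, which neither document specifies. It is a difference in expectation: a replacement may also fail, so not every observed rate need rise. The frequency of the event is an assumption and may be low. The point is minor, a wording repair that should be made before outcomes are reviewed.

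**What to change.** 1. In paragraph 2 of Protocol 8.2.1 and the matching paragraph of SAP 5.c, add that patients removed for hypersensitivity reactions that are grade 3-4 and related to study treatment are not replaced, stay in the efficacy denominator despite fewer than 5 doses, and count as non-responders.
2. Make the replacement sentence in Protocol 6.7 refer to 8.2.1, so that it no longer overrides the exception.
3. Reconcile the analysis set named in Protocol 10.2 with SAP 5.c, stating which set serves which endpoint.

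Deleting the mention of hypersensitivity from paragraph 2 is not enough. Paragraph 3 would then govern replacement, but it does not say whether a patient who is not replaced is evaluable or how that patient is scored.

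Cost: one clause in each document, a cross-reference in 6.7 and a sentence in 10.2. The reported efficacy rates may be slightly lower.
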